1. INTRODUCTION

Enhancement of the anti-tumor immune response with immunotherapy agents has emerged as a highly effective and complementary approach to the therapeutic mainstays of surgery, cytotoxic chemotherapy, targeted drugs and radiation therapy. More recently, the induction of lasting responses and dramatic tumor regression suggests that immunotherapy may convert previously fatal diseases into chronic manageable situations.

The theory of immune surveillance and immunoediting is a dynamic process involving immune recognition and elimination of cancer, an equilibrium state and at times evasion of cancer from immune system control (1-3). Immune system avoidance and escape is now a recognized hallmark feature of cancer progression and carcinogenesis and the increased rates of lymphoma, sarcoma, and cervical cancer in immunocompromised individuals support the notion that immunoediting is essential for cancer suppression in humans (2), (4).

Under chronic stimulation, T cells lose proliferative and effector function capacity, often due to signal down-modulation via the increased expression of proteins such as PD-1, an inhibitory checkpoint receptor of the CD28 receptor family (5). The ligand for the PD-1 receptor, PD-L1, is expressed in a variety of human malignancies, and its high level of expression has been previously correlated with poor patient prognosis and resistance to treatment in non-small-cell lung cancer, glioblastoma multiforme, and squamous-cell carcinoma of head and neck (6-8)]. Binding of ligand (PD-L1 or PD-L2), often expressed on tumor cells, to PD-1 imparts an inhibitory signal to the T cell, thus down-modulating the anti-tumor T-cell response (9).

Blockade of the PD-1/PD-L1 T-cell checkpoint pathway is an effective and well tolerated approach to stimulating the immune response, and has achieved significant objective responses in advanced, melanoma, renal cell cancer (RCC), and NSCLC (10). However, optimal therapy will likely require combining anti-PD-1 monoclonal antibody (mAb) treatment with conventional therapies and novel immunotherapy approaches. Combination approaches to stimulate convergent aspects of host immunity by employing complementary immunomodulators as well as immune-stimulatory aspects of conventional modalities such as radiation and chemotherapy may result in the development of more effective cancer therapies.

1.1 RADIATION THERAPY AND IMMUNOGENICITY

The abscopal effect is a well described phenomenon in which tumor regression is observed outside of a radiation treatment field after radiation therapy. It is thought to be immune mediated and has sparked interest in multi-modal therapies (11-13). Radiotherapy is known to induce immunogenic cell death in cancer cells, marked by the expression of molecules that elicit "damage-associated molecular patterns" (DAMP's) (14). Chemokines and cytokines such as IL-1B and TNF-A, as well as heat shock protein 70 (HSP70), high mobility group box 1 protein (HMGB1) and adenosine triphosphate (ATP) serve to recruit dendritic cells. Also, DAMP's

induce maturation of dendritic cells enabling antigen presentation, and subsequently the development of an appropriate adaptive immune response (15, 16). Likewise, radiotherapy has been shown to induce the expression of the antigen-presenting molecule MHC-1 as well as *de novo* transcription and up-regulation of tumor antigen proteins in lung cancer cell lines. These cells show increased expression of tumor specific antigen and antigen-presenting complexes and demonstrate increased susceptibility to cytotoxic T-cell killing (17).

Radiation therapy may sensitize tumor cells to immune-mediated attack by releasing soluble tumor antigens from killed cells and increasing tumor cell surface expression of antigens and receptors mediating T-cell recognition and killing (18). Pre-clinical studies have demonstrated that ablative radiotherapy delivered in a hypofractionated regimen more frequently produces an abscopal effect, especially when combined with immunotherapy compared to conventionally fractionated radiation therapy (19). Researchers have speculated whether conventionally fractionated radiation therapy impairs immune response due to increased killing of circulating lymphocytes and reducing immune mediated cancer killing (20). In a pre-clinical mouse model of metastatic breast carcinoma, three doses of 8Gy was superior to a single dose of 20Gy or 5 doses of 6Gy of irradiation in inducing an abscopal effect in mice treated with a CTLA-4 blocking monoclonal antibody (19). Lee et al. showed that ablative doses of radiation correspond to greater levels of dendritic cell maturation and T-cell priming in draining lymph nodes in a mouse model of melanoma (21). Taken together, there is increasing evidence that ablative radiation treatment can produce an individualized "in situ vaccine" against the tumor cells that could work in concert with immunotherapy (22-24).

"Antigen cascade" is a term used to describe the process in which vaccination against a particular tumor antigen results in the acquisition of novel tumor antigens and activity of the immune system toward these newly discovered antigens (25). Antigenic cascade has been observed in preclinical mouse models as well as in human studies (26, 27). Antigenic cascade has been suggested as an essential component of abscopal tumor regression and that radiation therapy, by inducing an immunogenic cell death, when coupled with immunotherapy, can potentially cause polyclonal T-cell responses to a variety of tumor antigens through antigenic cascade leading to a robust immune response against tumor tissues that harbor these antigens (27).

T-regulatory (T-reg) cell representation in the tumor microenvironment after radiation therapy is a known phenomenon (20). Following sublethal irradiation of antigen-primed mice, antigen-specific immune suppression mediated primarily by T-regs develops over several weeks (18). The influx of T-reg cells into an irradiated tumor microenvironment therefore may counteract any benefit obtained from increased antigen release, enhanced antigen presentation, or influx of T effector cells. This observation is often used to suggest that radiation therapy impedes a vigorous immune response since T-reg cells promote tolerance of the immune system toward tumor cells (24),(28, 29). However, the increased presence of T-reg cells following SBRT in the

tumor microenvironment does not correlate with increased immunosuppression. In fact, functional analysis of these T-reg cells reveal impairment and inability to prevent T cell proliferation (30).

These studies suggest high dose hypofractionated radiation abrogates immune system suppressive responses to conventional fractionated radiation therapy creating a prime opportunity for enhanced tumor response when combining SBRT with immune modulating agents. Given the improved outcomes with immunotherapy relative to cytotoxic chemotherapy, it is plausible that enhanced response with combined modality approaches could yield further improvements in clinical outcomes.

1.2 RATIONALE FOR ANTI-PD1 BLOCKADE.

PD-1 is a cell surface molecule frequently expressed on the surface T-cells. It functions as an immune checkpoint and down regulates the immune system by preventing activation and proliferation of T-cells by increasing programmed cell death in cytotoxic T-cells and upregulating T-reg cells (31). Tumor cells have been shown to upregulate PD-1 ligand (PD-L1) expression as a mechanism of immune system evasion. Hence, PD-L1 expression by tumor cells contributes to immune system evasion by tumors (32). As such, PD-1 blockade is an obvious immunotherapy target and has been demonstrated as an effective approach to overcome cancer mediated immunosuppression.

Within the past several years, several groups have employed the use of radiotherapy with PD-1/PD-L1 signaling inhibition in mouse models with remarkable results. Ablative radiotherapy combined with PD-1 inhibition promoted tumor-associated antigen / MHC complex formation and subsequent antigen cross-presentation within lymph nodes followed by cytotoxic T-cell infiltration into tumors in a mouse model of melanoma (33). In a mouse model of intracranial glioma, combination radiation therapy and anti-PD-1 blockade resulted in increased number of killer T-cells and decreased T-reg cell infiltration in tumors when compared to either therapy alone (34). Moreover, up to 40% of mice treated with combination therapy survived longer than 90 days compared to ~ 30-day survival for either treatment alone and these "cured" mice also developed long-term immunity and were resistant to re-inoculation with tumor cells.

PD-1 expression by tumor cells prevents immune system recognition of distant metastases (35). In this mouse model study of metastatic melanoma, PD-1 inhibition resulted in a 66% reduction in secondary non-irradiated tumors 20 days after a single ablative dose radiation. A single dose of 15Gy was chosen since this therapy is representative of SBRT aimed at controlling oligometastatic disease in humans.

2.0 PROPOSED TRIAL RATIONALE

Anti-PD-1 antibodies have demonstrated activity in the treatment of lung cancer. Opdivo was approved in February of 2015 by the FDA for patients with metastatic squamous NSCLC with progression on or after platinum based therapy. In the open-label trial, patients were randomized to receive OPDIVO (n=135) administered at 3mg/kg every 2 weeks. Median survival was improved to 9.2 months compared to 6 months in patients receiving docetaxel (n=137) 75mg/m² every 3 weeks, p=0.00025. Median progression free survival was slightly improved to 3.5 months compared to 2.8 months but 1 year overall survival was improved to 42% compared to 24% (36).

We expect that improvements in local control, increased immunogenic response and abscopal effect seen with combined modality treatment will result in improved local control, progression free survival and resultant significant increases in overall survival beyond 3 months. We propose a pilot/phase II study to assess the safety and efficacy of combination immunotherapy and stereotactic ablative radiation therapy (I-SABR).

Treatment will be a sequential combination treatment of SABR/SBRT and immunotherapy to assess the safety and feasibility of treatment. SABR/SBRT will be administered in 3-5 daily treatments followed by immunotherapy following the conclusion of SABR/SBRT. This approach will take advantage of the transient increase in antigen availability, increased antigen presentation and upregulation of PD-1 by tumor cells following ablative radiation therapy. After an interim safety analysis, the study will continue to the phase II portion where overall survival, progression free survival and response rate will be the primary and secondary end points. For reference, outcomes will be compared to the immunotherapy arms of checkmate 057 and Keynote 042 trials.

Several trials examining combination I-SABR are currently underway. A table of selected studies is included in [Table 1](#).

Study (Institution)	SABR Target	Dose (Gy/Fractionation)	Immunotherapy Agent	Sequence
NCT02239900 (MD Anderson Cancer Center)	Liver Lung Adrenal	50/4 60/10	Ipilimumab	Concurrent/Sequential
NCT01862900 (Chiles Research Institute)	Lung Liver	15/1 201/1	Anti-OX40	Concurrent
NCT01769222 (Stanford University)	Any	20/2	Ipilimumab	Concurrent
NCT02298946 (NIH/NCI)	Liver	8/1 24/3	PD-1 Inhibitor	Sequential

Table 1. List of selected ongoing I-SABR studies

2.1 RATIONALE FOR DOSE SELECTION

A. Radiation Therapy: All patients in this trial will be treated with fractionated Stereotactic body radiation therapy. Treatment of oligometastatic lung cancer in this fashion has been explored in multiple studies with encouraging long term survival data (37-39). In a recent multi-institutional randomized trial from MD Anderson cancer center, patients with oligometastatic lung cancer where randomized to systemic therapy plus SBRT to all metastatic sites versus systemic therapy alone (40). The study was terminated early after a planned interim safety analysis showed significantly improved in progression free survival in the SBRT group (11.9 vs 3.9 months) at median follow up of 12 months. Patients in the SBRT group were less likely to develop new lesions compared to patients on systemic therapy alone suggesting SBRT acted similarly to systemic therapy.

In a series of mouse tumor models treated with an anti-CTLA-4 antibody combined with 3 different radiation regimens, enhanced tumor responses were observed when treated with fractionated radiation regimens of $8 \text{ Gy} \times 3$ or $6 \text{ Gy} \times 5$ administered on consecutive days, but not with $20 \text{ Gy} \times 1$ (19). The fractionated regimens, but not the single radiation dose, also resulted in abscopal effects. For uniformity, we will adhere to the radiation dose guidelines as prescribed in the NRG-BR001 protocol examining the role of SBRT for oligo-metastatic disease (41). Dose reductions are allowed to pre-specified doses at the treating physician's discretion if dosimetric criteria are not achievable. Dose schedules and prescriptions are described under radiation treatment.

B. Immunotherapy: All patients in this trial will be treated with either Nivolumab or Pembrolizumab at FDA approved dosing and indications (1, 36). If new FDA approved anti-PD-1 therapies emerge during the study duration, the study will be modified with IRB approval to allow addition of newly approved therapies to the protocol. (36). These FDA approved dosing schedules are established and have a favorable toxicity profile and will allow direct comparison of outcomes to immunotherapy alone trials vs immunotherapy plus SBRT.

3. STUDY OBJECTIVES

3.1 Primary Objectives

The primary objective of the pilot phase of the study is to characterize the safety, feasibility and tolerability of sequential combination I-SABR in patients with metastatic NSCLC. The first 20 patients will be evaluated for 15 weeks following treatments with I-SABR prior to continuing enrollment. In the Brahmer trial, 5% of patients in the Nivolumab arm developed pneumonitis with a median time to onset of treatment related pulmonary events of 15 weeks. All but one patient with pulmonary events were treated with glucocorticoids and all cases resolved with a median time to resolution of 5 weeks (range 0.6-12.1 weeks).

If more than 5% of patients develop grade ≥ 3 pneumonitis during the initial evaluation phase, no lung directed therapy will be permitted during the phase II portion.

The primary objective of the phase II portion of the study will be overall survival.

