3.2 Secondary Objectives

The secondary objectives of the study are

1. To determine the progression free survival measured from time of enrollment to first evidence of progressive disease and evaluated 3 months after treatment initiation.
2. To determine the local control measured from time of enrollment to first evidence of progressive disease at the treatment site and evaluated 3 months after treatment initiation
3. To determine the incidence of grade ≥ 3 , pneumonitis 6 months of completing SBRT
4. To determine the influence of number of metastatic sites on OS, and PFS.

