4.3 Immunotherapy

Immunotherapy will be delivered in the form of PD-1/PD-L1 blockade using approved anti PD-1/PD-L1 agents. Dose reductions are appropriate for toxicity as specified or at the discretion of the treating medical oncologist. Prior immunotherapy as part of multi-drug therapy or monotherapy is acceptable prior to initiation of SBRT.

The DLT observation period for continuation or discontinuation of therapy is defined as 14 days starting with cycle 1, day 1. To be evaluable for DLT, a patient must have received at least the first 2 administrations and be monitored for at least 14 days following the first administration. Any of the below outlined events occurring during each DLT observation period and considered to be at least possibly related to Nivolumab will qualify as a DLT.

Non-Hematologic Toxicity

1. Grade ≥ 2 uveitis
2. Any Grade ≥ 3 non-hematologic toxicity except
 - a. Nausea, vomiting or diarrhea
 - b. Clinically insignificant laboratory abnormalities
 - c. Grade 3 infusion reactions that respond to medical management
 - d. Grade 3 immune related effects other than uveitis that improve within 7-14 days with steroid treatment (Appendix 1).

Hematologic Toxicity

1. Grade 4 neutropenia lasting more than 1 week
2. Grade 4 thrombocytopenia
3. Grade 3 thrombocytopenia with bleeding
4. Grade ≥ 3 febrile neutropenia

Special

1. Grade ≥ 2 pneumonitis

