4.4 Duration of Study

The study will conclude 24 months after the last patient is accrued. Given the poor prognosis and short overall survival in patients with metastatic NSCLC, all end-points should be realized within 24 months. At the conclusion of the study, patients and investigators may decide to continue with Immunotherapy treatment. We expect to enroll 100 patients over 2 years.

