5.3 Sample Size

More than 350 patients with metastatic lung cancer present to the Crozer-Keystone health system for treatment annually. If 50% of patients are eligible for this study, we expect approximately 100 patients will enroll and be treated on this study. Patients will be followed for 2 years on the study. The study will conclude 2 years after the last patient is enrolled. An interim safety and feasibility analysis will be performed on the first 20 patients in the pilot phase. Overall survival, progression free survival, local control and subgroup analysis will be performed on the entire patient cohort at the conclusion of the study.

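### The pneumonitis rule in Section 3.1 takes effect only in phase II even when its trigger is settled during the pilot, and no trial-level criterion in the text shown covers cases outside its one 20-patient evaluation

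*Protocol*

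**What the plan says.** Section 3.1 sets the pilot evaluation: "The first 20 patients will be evaluated for 15 weeks following treatments with I-SABR prior to continuing enrollment". The trigger is "If more than 5% of patients develop grade ≥ 3 pneumonitis during the initial evaluation phase", and the consequence is confined to what comes next: "during the initial evaluation phase, no lung directed therapy will be permitted during the phase II portion".

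Section 5.3 describes one safety look: "An interim safety and feasibility analysis will be performed on the first 20 patients in the pilot phase". Section 4.4 gives the size and pace: "We expect to enroll 100 patients over 2 years". Eighty patients therefore enter after that look.

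For the whole study, severe pneumonitis appears again only as item 3 of Section 3.2: "To determine the incidence of grade ≥ 3 , pneumonitis 6 months of completing SBRT". No threshold or action is attached to it.

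The reference figures in Section 3.1 are that "5% of patients in the Nivolumab arm developed pneumonitis with a median time to onset of treatment related pulmonary events of 15 weeks".

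Other provisions concern the individual patient. Section 4.3 counts grade 2 or worse pneumonitis as a dose-limiting toxicity and says "The DLT observation period for continuation or discontinuation of therapy is defined as 14 days starting with cycle 1, day 1". Appendix I covers holding or discontinuing immunotherapy in a patient with pneumonitis. Section 8.2 describes routine adverse event reporting and refers to an Appendix IV, which is not in the text at hand.

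**The concern.** The rule has two gaps in time.

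The first is inside the pilot. The denominator is fixed at 20, so two cases are enough to exceed 5% and nothing later can reverse that. The consequence nevertheless waits for phase II. Enrolment pauses after patient 20, not before, so a patient who enters the pilot after the second case can still receive the treatment component that the protocol has, by its own test, decided to withdraw.

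The second is after the pilot. The trigger counts only cases in the initial evaluation. A case in a pilot patient after week 15, or in any of patients 21 to 100, feeds an incidence estimate but is compared with no limit. What is at stake is that a materially raised rate of severe pneumonitis passes a look at 20 patients and is then not tested again at trial level.

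**Working it through.** **Inputs from the protocol.** 20 patients at the look, trigger above 5%, 15-week evaluation, reference median onset 15 weeks (Section 3.1). One look (Section 5.3). 100 patients over 2 years (Section 4.4), which is 100/104 = 0.96 per week. The protocol states no error rate or power for this rule, so there is no figure of its own to reproduce.

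**Assumptions.** The true rate of grade 3 or worse pneumonitis on the combination is not given; 5% to 20% is shown for the look, and 10% to 30% for the pilot delay. All enrolled patients are treated as at risk.

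**Step 1: the trigger as a count.** 1/20 = 5.0% is not above 5%; 2/20 = 10% is. The trigger is 2 or more cases.

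**Step 2: chance that the look does not trigger.** P(X ≤ 1) = (1−p)^20 + 20p(1−p)^19. At p = 10%: 0.122 + 0.270 = 0.392.

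| True rate | No trigger, all events seen by week 15 | No trigger, half seen by week 15 | Expected cases in 80 later patients (80p) |
|---|---|---|---|
| 5% | 74% | 91% | 4 |
| 10% | 39% | 74% | 8 |
| 15% | 18% | 55% | 12 |
| 20% | 7% | 39% | 16 |

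The third column replaces p by p/2. It applies the cited 15-week median to this regimen, which is an assumption.

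**Step 3: what a pass rules out.** The exact two-sided 95% upper limit for 0/20 is 1 − 0.025^(1/20) = 16.8%. For 1/20 it is 24.9% (the 97.5% point of a Beta(2, 19) distribution).

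**Step 4: pilot patients who start after the second case.** At 0.96 per week the twentieth patient enters 19/0.96 = about 20 weeks after the first. Simulation with evenly spaced entry, treatment at entry and only onsets within 15 weeks counted, among pilots that trigger:

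| True rate | Mean, onset uniform over 15 weeks | Mean, exponential onset with median 15 weeks | At least one such patient |
|---|---|---|---|
| 10% | 3.2 | 2.8 | 52–58% |
| 20% | 5.3 | 3.8 | 62–78% |
| 30% | 7.4 | 4.9 | 73–92% |

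**Step 5: would repeating the 5% threshold be enough?** More than 5% means at least 2, 3, 4, 5 and 6 cumulative cases at 20, 40, 60, 80 and 100 patients. Exact sequential binomial calculation, with all outcomes taken as known at each look, gives the chance of ever crossing:

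| True rate | Single look at 20 | Repeated at 20, 40, 60, 80, 100 |
|---|---|---|
| 5% | 26% | 56% |
| 10% | 61% | 97% |
| 15% | 82% | 99.9% |

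At a true 5%, the rate cited for nivolumab alone (with no grade given), the repeated bare threshold would trigger more often than not.

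**Step 6: onset lag.** At 0.96 per week, about 15 × 0.96 = 14 patients at any later look would have less than 15 weeks of observation unless enrolment pauses again. The repeated-look figures in Step 5 ignore this.

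**The case against.** The strongest defence is that a safety run-in followed by routine monitoring is a coherent, if weak, design. No two passages contradict each other, and no stated operating characteristic is wrong. Enrolment does pause for the 15-week evaluation, and if the look triggers, patients 21 to 100 are covered by the ban. This stands, and it limits the severity.

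A reader might infer that severe pneumonitis could build up with no action at all. The protocol does not support that: Section 4.3 defines a dose-limiting toxicity and Appendix I provides for holding or discontinuing immunotherapy. These act on the affected patient, after SBRT has been given, and set no limit for the patients who follow. Nor can it be said that the protocol certainly has no other trial-level trigger, since Appendix IV is not shown.

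A reader might also take the 8 or 12 expected cases at 10% or 15% as preventable harm. They are not. The rule withdraws lung-directed therapy only, while immunotherapy continues, and Section 3.1 itself reports pneumonitis on nivolumab alone. Section 6.1 allows many non-lung targets and at most one lung lesion, and the share of patients receiving lung SBRT is not stated. If that share is small, 20 enrolled patients say even less about the risk in question.

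Finally, it is tempting to supply ready-made stopping counts. Counts with a low false-trigger rate would have to abandon the 5% threshold, and repeating that threshold costs 56% at a true 5%. The choice belongs to the sponsor.

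**Conclusion.** The concern holds as a flaw in the timing and reach of the one trial-level pneumonitis rule in the text shown. Given a trigger, about 3 pilot patients on average start treatment after the second case at a true 10%, and about 5 to 7 at 30%. At 10%, though, over 40% of triggered pilots have none. If the look passes, nothing at trial level tests the rate again. The probability of passing is 39% at a true 10% and 18% at 15%, and higher if events fall after week 15. The binomial figures are exact for the assumed rates; the pilot counts also depend on the assumed onset pattern and steady accrual. The documents support a cheap improvement that should be made. They do not support a claim of uncontrolled harm or of a rule that contradicts another passage.

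**What to change.** Amend Section 3.1 in two respects.

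1. Reconcile the timing of the rule with its own trigger: the consequence already written there should take effect when the trigger is met, not only at the start of phase II.
2. State that cumulative review of grade 3 or worse pneumonitis continues after patient 20, including late pilot cases, against a pre-specified criterion. The sponsor should choose the criterion and report its trigger probabilities over a range of true rates, allowing for onset lag and for how many patients receive lung-directed therapy.

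If Appendix IV already holds such a criterion, Section 3.1 should refer to it.

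The cost is a short amendment. The events are already collected, so no extra patients or procedures are needed. The downside is some added chance of a false trigger, its size depending on the criterion. Requiring complete 15-week follow-up at each later look would also mean further enrolment pauses.
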